8.2. Planned Analyses

8.2.1. Interim Analysis

Prior to the final analysis, interim analyses may be conducted, and the analyses may be submitted to regulatory agencies to seek guidance for the overall clinical development program.

8.2.2. Primary Analysis

The primary analysis will be conducted after all patients have discontinued the study or have been on study for at least 24 weeks and completed the Week 24 response assessments, outstanding data queries have been resolved or adjudicated as unresolvable, and the data have been cleaned and finalized for the analysis.

8.2.3. Final Analysis

The final analysis will be performed after all patients have discontinued the study, outstanding data queries have been resolved or adjudicated as unresolvable, and the data have been cleaned and finalized.

8.3. Analysis Conventions

8.3.1. Analysis Sets

8.3.1.1. Efficacy

The primary analysis set for efficacy analysis is the Full Analysis Set (FAS). The FAS includes all enrolled patients who receive at least 1 dose of any study treatment, with treatment group designated according to the assigned treatment.

8.3.1.2. Safety

The primary analysis set for safety analyses is the Safety Analysis Set. It includes all patients who receive at least 1 dose of study treatment, with treatment assignments designated according to the actual treatment received. This analysis set will be used in the analyses of safety endpoints, as well as study treatment administration. All data collected during treatment up to 70 days (± 7 days) after treatment discontinuation will be included in the safety summaries.

The DLT Evaluable Analysis Set includes all patients in the Safety Analysis Set who are enrolled in the safety run-in cohorts, have safety assessments through the protocol-specified DLT assessment window (first 4 weeks of study dosing, inclusive), and fulfill the criteria for evaluation for DLT specified in Section 3.1.1.

Safety assessments relevant to the DLT Evaluable Analysis Set definition include laboratory serum chemistry tests and hematology tests as specified in Section 3.1.1. The RP2D will be based on the DLT Evaluable Analysis Set.

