3.1.1. Safety Run-in Cohorts

This study will include the following 3 safety run-in cohorts:

- Safety Run-in Cohort 1 (1L Unfit AML Mag+Ven+Aza), closed to enrollment globally as of Protocol Amendment 5: magrolimab + venetoclax + azacitidine in patients with newly diagnosed, previously untreated AML who are ineligible for intensive chemotherapy
- Safety Run-in Cohort 2 (R/R AML Mag+MEC): magrolimab + MEC in patients with R/R AML
- Safety Run-in Cohort 3 (Post-chemo Maint Mag+CC-486), closed to enrollment globally as of Protocol Amendment 5: magrolimab + CC-486 as maintenance therapy in patients with newly diagnosed AML who are in CR or CRi with MRD positivity following intensive chemotherapy

Initially, 6 patients will be enrolled into Safety Run-in Cohorts 1, 2, and 3 to receive study treatment according to the dose levels presented in Table 1, Table 2, or Table 3, respectively. A DLT assessment period of 1 cycle (28 days) will occur. The DLT assessment period and definition are provided in Sections 3.1.1.1 and 3.1.1.2.

Dose de-escalation decisions will be made as follows:

- If no more than 2 patients in a safety run-in cohort experience a DLT in Cycle 1, enrollment into the corresponding Phase 2 cohort will begin at this dose level.
- If 3 or more (> 33%) patients in a safety run-in cohort experience a DLT up to the end of Cycle 1, another 6 patients will be enrolled in that cohort at a lower dose and evaluated in the same manner to define the RP2D.

De-escalation dose levels for each safety run-in cohort are presented in Table 4, Table 5, and Table 6. Any dose de-escalation for Cohorts 1 and 3 will occur with the combination regimen, as there is a lack of dose-dependent toxicities observed with magrolimab in over 500 patients treated to date with magrolimab as monotherapy or in combination, and agents being evaluated in combination with magrolimab have identified or potential dose-related toxicities as cytotoxic agents (ie, venetoclax and CC-486). For Cohort 2, any dose de-escalation will occur with magrolimab, as the combination with chemotherapy (ie, MEC) has not been extensively studied. The selected RP2D for any cohort cannot exceed the identified MTD for that cohort.

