3.1.1.1. DLT Assessment Period

The DLT assessment period is the first cycle (28 days). For patients who are being evaluated for prolonged myelosuppression (Section 3.1.1.2), the 28-day DLT assessment period will extend to 42 days for Safety Run-in Cohorts 1 and 2. Patients are considered evaluable for assessment of a DLT if either of the following criteria is met in the DLT assessment period:

- The patient experienced a DLT at any time after initiation of the first dose of study treatment.
- The patient did not experience a DLT and completed at least 4 infusions of magrolimab and at least 14 doses of venetoclax and 5 doses of azacitidine (Safety Run-in Cohort 1), at least 3 days of dosing with MEC (Safety Run-in Cohort 2), or at least 10 doses of CC-486 (Safety Run-in Cohort 3).

If a patient experiences a DLT during the DLT assessment period, the investigator should contact the medical monitor to discuss whether the patient can remain on study drug.

Patients who are not evaluable for DLT will be replaced in the safety run-in cohorts.

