3.1.1.2. DLT Definition

All toxicities will be graded according to the NCI CTCAE Version 5.0. A DLT is defined as any Grade 4 or higher hematologic toxicity or Grade 3 or higher nonhematologic toxicity (that has worsened in severity from pretreatment baseline) during the 4-week DLT assessment period and is related to magrolimab or magrolimab combination.

The following are exceptions to the DLT definition and are NOT considered DLTs:

- Myelosuppression (Grade 4 neutropenia and thrombocytopenia) lasting no longer than 42 days from the start of study treatment for Cohorts 1 and 2, and no longer than 21 days from the start of study treatment for Cohort 3. Complications within the first 4 weeks that are associated with myelosuppression, such as fevers, infections, bleeding, and related hospitalizations, will also not be considered DLTs. However, Grade 4 neutropenia or thrombocytopenia lasting longer than 42 days from the start of study treatment for Cohorts 1 and 2, or 21 days from the start of study treatment for Cohort 3, without evidence of leukemia, will be considered DLTs. Absence of residual disease must be verified by peripheral blood count and bone marrow aspirate and biopsy at Day 43 (+ 10 days) for Cohorts 1 and 2.
- Grade 3 indirect/unconjugated hyperbilirubinemia that resolves to ≤ Grade 2 or pretreatment baseline with supportive care within 7 days and is not associated with other clinically significant consequences.
- Grade 3 isolated electrolyte laboratory abnormalities that resolve to ≤ Grade 2 or pretreatment baseline with supportive care within 7 days and are not associated with other clinically significant consequences.

- Grade 3 elevation in alanine aminotransferase (ALT), aspartate aminotransferase (AST), or alkaline phosphatase (ALP) that resolves to ≤ Grade 2 or pretreatment baseline with supportive care within 7 days and is not associated with other clinically significant consequences.
- Grade 3 nausea, vomiting, or diarrhea that resolves to ≤ Grade 2 or pretreatment baseline with supportive care within 7 days.
- Grade 3 fatigue that resolves to ≤ Grade 2 or pretreatment baseline within 2 weeks.
- Grade 3 magrolimab IRRs in the absence of an optimal pretreatment regimen, which is defined as acetaminophen or a comparable non-steroidal anti-inflammatory agent, plus an antihistamine and corticosteroids.

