4.1.1. Patient Replacement

For the safety run-in cohorts, patients who do not meet the DLT assessment criteria will be replaced. In the Phase 2 cohorts, there will be no patient replacement.

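### The DLT Evaluable Analysis Set can leave out patients who had a DLT, and the protocol's DLT windows and bases for the RP2D do not agree

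*Protocol*

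**What the plan says.** **The set.** Protocol Section 8.3.1.2 puts two joint conditions on a treated run-in patient who is to enter the DLT Evaluable Analysis Set, namely to "have safety assessments through the protocol-specified DLT assessment window (first 4 weeks of study dosing, inclusive), and fulfill the criteria"; these criteria are those of Section 3.1.1. It names serum chemistry and hematology tests among the relevant assessments. It then states: "The RP2D will be based on the DLT Evaluable Analysis Set". The synopsis joins the same two conditions by 'and', without the 4-week parenthesis.

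**Evaluability.** Section 3.1.1.1 calls a patient evaluable "if either of the following criteria is met in the DLT assessment period". There are two such criteria, and one of them is a DLT alone: "The patient experienced a DLT at any time after initiation of the first dose of study treatment". The other is minimum dosing completed without a DLT. Under Section 4.1.1, run-in "patients who do not meet the DLT assessment criteria will be replaced".

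**Windows.** The period is 28 days. Where prolonged myelosuppression is in question, "the 28-day DLT assessment period will extend to 42 days for Safety Run-in Cohorts 1 and 2". Section 3.1.1.2 places DLTs in a 4-week period, yet also makes Grade 4 neutropenia or thrombocytopenia "lasting longer than 42 days from the start of study treatment for Cohorts 1 and 2", without evidence of leukemia, a DLT. Absence of disease is verified at Day 43 (+ 10 days).

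**Decision.** Section 3.1.1 opens Phase 2 "If no more than 2 patients in a safety run-in cohort experience a DLT in Cycle 1" and de-escalates at 3 or more, counted to the end of Cycle 1. Section 3.1.1.2 ends by basing the Phase 2 dose on all relevant clinical and PK data from all treated run-in patients.

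**The concern.** A DLT is complete information for the dose decision as soon as it happens. Requiring later assessments from a patient who has already had one adds nothing, and it selects against the patients whose toxicity ended their follow-up. A completion condition makes sense only for patients without a DLT, to show that they were observed long enough. Section 8.3.1.2 applies it to everyone.

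The windows raise a second question. The definition recognises a late cytopenia DLT in Cohorts 1 and 2, but the counting rule and the set are worded for the first 28 days. A reader cannot tell whether the dose decision waits for that event.

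The incidence of DLTs is a primary endpoint of the run-in (Section 8.1.2), and the decision is made on 6 patients. One patient more or less can change it.

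**Working it through.** The plan gives no figure to reproduce here. The check is set logic and day arithmetic.

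**1. Set logic.** Let D = had a DLT, M = completed minimum dosing without a DLT, A = has safety assessments through Week 4.

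- Section 3.1.1.1: evaluable = D or M.
- Section 8.3.1.2 and synopsis: in the set = A and (D or M).
- Evaluable but outside the set = (D or M) and not A. This includes every DLT patient without assessments through Week 4.

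**2. Can this happen without death or withdrawal?** Yes, on scheduled tests alone.

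- Permanent discontinuation of study treatment follows a Grade 4 infusion-related reaction (Table 15) or Grade 3 to 4 pneumonitis (Section 7.8.1.6). Neither is among the DLT exceptions in Section 3.1.1.2, so if treatment-related each is a DLT.
- After treatment stops, Appendix Table 9 schedules CBC and chemistry only at the end-of-treatment visit. The 30-day and 70-day contacts have neither.
- Section 3.4 places that visit within 7 days (± 7) of the last dose or of the decision to stop, whichever is later. That is at most 7 + 7 = 14 days after.
- With the last dose and decision on Day 1, the last scheduled test is by Day 1 + 14 = Day 15. For Day 8 it is by Day 22. Both precede Day 28.

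**3. Effect on the count.** Suppose 3 of 6 have a DLT (50%) and one of the three is outside the set.

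- In the set: 2 of 5 = 40%.
- By count, 2 is no more than 2, so Phase 2 opens. By the percentage attached to the de-escalation rule (> 33%), 40% is above the limit. With five patients, the two forms of the rule disagree.
- Generally, removing one DLT patient changes k/n to (k − 1)/(n − 1), which is smaller whenever k < n.

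**4. Windows, Cohorts 1 and 2.**

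| Place | Period |
|---|---|
| 3.1.1, counting rule | Cycle 1, 28 days |
| 3.1.1.2, general definition | 4 weeks |
| 8.3.1.2, set | first 4 weeks |
| 3.1.1.1, extension | 42 days |
| 3.1.1.2, late cytopenia | more than 42 days; verified Day 43 to 43 + 10 = 53 |

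The late DLT exists on Day 43 at the earliest. That is 43 − 28 = 15 days after the 28-day limit and 43 − 42 = 1 day after the extended one. Cohort 3's threshold is 21 days and fits within 28.

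**5. Illustration only.** Assume a true DLT rate p and a share q of DLTs that are not counted, either because the patient is outside the set or because the event is late. Assume nobody is replaced and the threshold stays at 3. The counted number is then Binomial(6, p(1 − q)). P(3 or more) is:

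| p | q = 0 | q = 0.10 | q = 0.25 | q = 0.50 |
|---|---|---|---|---|
| 0.40 | 0.456 | 0.373 | 0.256 | 0.099 |
| 0.50 | 0.656 | 0.558 | 0.404 | 0.169 |

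Both p and q are assumptions; the documents give neither. The table shows direction and sensitivity, not an expected effect.

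**The case against.** Several stronger readings are tempting, and the text does not support them.

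- **That excluded DLT patients will be replaced.** A reader might infer this and expect the run-in to be refilled with patients who tolerate treatment. Sections 3.1.1.1 and 4.1.1 tie replacement to evaluability, not to membership of the set. A patient with a DLT is evaluable, so on that wording is not replaced.
- **That the set cannot count the late cytopenia DLT.** The set selects patients, not events. A patient who completed minimum dosing and was assessed through Week 4 is in it, and a later DLT is still that patient's DLT. Section 8.3.1.2 also refers to Section 3.1.1, where the 42-day extension sits. What remains is doubt over whether the event is awaited and counted.
- **That the set alone fixes the RP2D.** The rule in Section 3.1.1 counts patients in the run-in cohort, and Section 3.1.1.2 draws on all treated run-in patients. The safety review team of Section 3.1.1.3 also assesses patient safety. An excluded patient's toxicity is therefore not hidden. But these provisions do not match the statement in Section 8.3.1.2, and the protocol does not say which governs.

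It is also fair that stopping drug is not the same as stopping assessments. Section 3.4 asks sites to keep such patients in follow-up and allows blood tests if clinically needed, so unscheduled tests may meet the condition. Myelosuppression-related complications in the first 4 weeks are exempt from DLT status, which narrows the early-death route. The number affected may be small or zero. This limits the size but does not remove the contradiction.

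**Conclusion.** The protocol is wrong as written on two points.

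1. Sections 3.1.1.1 and 8.3.1.2 define different groups of patients. For patients with a DLT the difference goes one way: they can be lost from the set, never gained. Losing one of three moves 3 of 6 to 2 of 5, across the count threshold if that threshold is applied to the set.
2. For Cohorts 1 and 2, none of the stated assessment periods reaches Day 43, when the protocol's own late cytopenia DLT can first be established. Three places use 28 days and one uses 42.

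The competing bases for the dose in Sections 3.1.1, 3.1.1.2 and 8.3.1.2 soften the first point and are themselves an inconsistency.

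The conclusion rests on a literal reading of 'and' in Section 8.3.1.2 and the synopsis. It does not rest on any assumed loss rate. The actual effect on the dose decision cannot be estimated from the documents. Cohort 1 is closed and Cohort 3 enrolled nobody, so the prospective relevance is to Cohort 2; the protocol does not report the status of its run-in. If that run-in is complete, the point still bears on how its primary DLT endpoint is reported.

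**What to change.** - In Section 8.3.1.2 and the synopsis, define the DLT Evaluable Analysis Set by the either/or criteria of Section 3.1.1.1, so that a patient with a DLT stays in the set whatever assessments follow. If an observation requirement is wanted, attach it only to patients without a DLT.
- Reconcile the DLT window across the synopsis and Sections 3.1.1, 3.1.1.1, 3.1.1.2 and 8.3.1.2, and state whether the cytopenia event verified at Day 43 (+ 10 days) enters the count for the dose decision. Which window applies is for the sponsor to decide.
- State one basis for the RP2D, or say how the DLT count in the set and the review of all treated run-in patients relate to each other.

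The cost is wording. The change to the set needs no extra patients, visits or tests. If the sponsor settles on a window longer than 28 days, the dose decision would wait only for patients still cytopenic at Day 28.

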8.3.1.3. Pharmacokinetics

The PK Analysis Set includes all enrolled patients who receive at least 1 dose of magrolimab and have at least 1 measurable posttreatment serum concentration of magrolimab.

8.3.1.4. Immunogenicity

The Immunogenicity Analysis Set includes all enrolled patients who receive at least 1 dose of magrolimab and have at least 1 evaluable anti-magrolimab antibody test result.

8.3.1.5. Biomarker

The Biomarker Analysis Set includes all enrolled patients who receive at least 1 dose of magrolimab and have evaluable baseline and postbaseline measurements to provide interpretable results for the specific parameter of interest.

8.3.1.6. Demographic and Baseline Characteristics

The All Enrolled Analysis Set includes all patients who receive a study patient identification number in the study after screening. This will be the primary analysis set for analyses of patient demographic and baseline characteristics, enrollment, and disposition.

8.3.2. Data Handling Conventions

By-patient listings will be created for important variables from each eCRF module. Summary tables for continuous variables will contain the following statistics: N (number in analysis set), n (number with data), mean, standard deviation, 95% CIs for the mean, median, minimum, and maximum. Summary tables for categorical variables will include: N, n, percentage, and 95% CIs for the percentage. Unless otherwise indicated, 95% CIs for binary variables will be calculated using the binomial distribution (exact method) and will be 2-sided. Data will be described and summarized by treatment cohort.

The baseline value used in each analysis will be the last (most recent) pretreatment value before or on the first dosing date of study treatment. As appropriate, changes from baseline to each subsequent time point will be described and summarized. Similarly, as appropriate, the greatest change from baseline during the study will also be described and summarized. Graphical techniques (ie, waterfall plots, Kaplan-Meier [KM] curves, line plots) may be used when such methods are appropriate and informative. Analyses will be based on observed data unless methods for handling missing data are specified. If there is a significant degree of non-normality, analyses may be performed on log-transformed data or nonparametric tests may be applied, as appropriate.

8.4. Demographic and Baseline Characteristics Analysis

Demographic and baseline measurements will be summarized using standard descriptive methods. Demographic summaries will include sex, race/ethnicity, and age. Baseline data will include a summary of body weight, height, body mass index, WHO AML classification, and ECOG performance status.

8.5. Efficacy Analysis

8.5.1. Primary Analysis

The point estimates of the CR rate and the corresponding 2-sided exact 95% CIs based on the Clopper-Pearson method will be provided for Cohorts 1 and 2. The MRD negative CR rate will be summarized similarly for Cohort 3. The CR and MRD negative CR data will also be tested against the historical control rates listed in Section 8.10 using 1-group Chi-square test for each cohort separately.

8.5.2. Secondary Analyses

The point estimates of the ORR, CR rate, CR/CRi rate, CR_{MRD} rate, cCR rate, and CR/CRh rate and the corresponding 2-sided exact 95% CIs based on the Clopper-Pearson method will be provided for Cohorts 1 and 2. The analyses of RBC and platelet transfusion independence rates (conversion rate and maintenance rate) will be similar to those of ORR.

Medians, first quartile (Q1), and third quartile (Q3) of EFS distribution, and the proportion of patients who are event free at Weeks 12, 24, and 48 from the first dosing date will be estimated by cohort using the KM method and the corresponding 95% CIs will be reported. Kaplan-Meier plots will be provided. Analyses of OS will be similar to those of EFS.

For the time-to-event endpoints of duration of CR, duration of CR/CRi, duration of CR/CRh, DOR, RFS, duration of MRD negative CR, and MRD negative CR/CRi, analyses will be conducted on the subsets for which the outcome measures are defined. Specifically, the duration of CR, duration of CR/CRi, duration of CR/CRh, and DOR will be based on patients in Cohorts 1 and 2 who achieve CR, CR/CRi, CR/CRh, and OR, respectively. The RFS will be analyzed for Cohort 3, duration of MRD negative CR will be based on patients in Cohort 3 who achieve MRD negative status and maintain CR, and the duration of MRD negative CR/CRi will be based on patients in Cohort 3 who achieve MRD negative status and maintain CR/CRi. The KM method will be used to estimate median durations and 95% CIs, and KM plots will be provided.

8.6. Safety Analysis

All safety data collected on or after the date that any drug in a study treatment regimen was first dosed up to the date of the last dose of any drug in a study treatment regimen plus 70 days (± 7 days) will be summarized by treatment group (according to the study drug received). Data for the pretreatment and treatment-free safety follow-up periods will be included in data listings. For categorical safety data, including incidence of AEs and categorizations of laboratory data, the number and percentage of patients will be summarized. For continuous safety data, including laboratory data, the number of patients, mean, standard deviation, minimum, quartiles, median, and maximum will be summarized.

8.6.1. Extent of Exposure

A patient's extent of exposure to study drug data will be generated from the study drug administration data. Exposure data will be summarized for each drug separately by treatment cohort.

8.6.2. Adverse Events

Clinical and laboratory AEs will be coded using the Medical Dictionary for Regulatory Activities (MedDRA). System organ class, high-level group term, high-level term, preferred term, and lower-level term will be attached to the clinical database.

Events will be summarized on the basis of the date of onset for the event. A treatment-emergent AE will be defined as any AE that begins on or after the date of first dose of study drug up to the date of last dose of study drug plus 70 days (\pm 7 days).

Summaries (number and percentage of patients) of treatment-emergent AEs (by system organ class and preferred term) will be provided by treatment group.

Adverse events that occurred before exposure to study treatment will be reported in data listings and appropriately identified as non-treatment-emergent AEs.

8.6.3. Laboratory Evaluations

Selected laboratory data (using conventional units) will be summarized using only observed data. Data and change from baseline at all scheduled time points will be summarized.

Graded laboratory abnormalities will be defined using the grading scheme in Appendix 4.

Incidence of treatment-emergent laboratory abnormalities, defined as values that increase at least 1 toxicity grade from baseline at any time point postbaseline, will be summarized by treatment group. If baseline data are missing, then any graded abnormality (ie, at least Grade 1) will be considered treatment emergent.

Laboratory abnormalities that occur before the first dose of study drug or after the patient has been discontinued from treatment for at least 70 days (± 7 days) will be included in a data listing.

